## 11.2 Study Population

The following study populations are defined and will be analysed as specified below. The population evaluable for safety will be the safety population.

The Intent to Treat (ITT) population: The total population of patients enrolled in the study

Safety population (evaluable for adverse events): All enrolled patients who received at least one dose of belumosudil

Efficacy population (evaluable for response): All enrolled patients who complete at least one cycle of belumosudil treatment with adequate baseline disease assessment.

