## 5. STUDY TREATMENT

### 5.1 Study Drug Administration

The Investigational Medicinal Product (IMP), Belmosudil, will be provided by Sanofi as 200 mg tablets.

Ruxolitinib will be dispensed as either 5 or 10 mg tablets, and will be obtained through the site's local pharmacy, as it will be administered per SOC.

All patients will receive open-label IMP. Responsibility for treatment of patients rests with the QI. Prior to initiating ruxolitinib (Cycle 1 Day 1), a tuberculosis skin test or interferon-gamma release assay should be performed in accordance with the approved JAKAVI® (ruxolitinib) product monograph to screen for latent tuberculosis infection, with results interpreted cautiously in immunocompromised patients. Positive results should prompt appropriate evaluation and management per institutional guidelines before starting isoniazid therapy. If the patient had been already treated with isoniazid prophylaxis for 6 months due to prior history of tuberculosis skin test or interferon-gamma release assay, this test will be exempted.

Eligible participants in this study will be started on ruxolitinib monotherapy orally at the standard recommended dose of 10 mg BID for 4 weeks (28 days). After one full cycle of ruxolitinib treatment (i.e., C2D1), the participant will have an AE assessment and, unless Grade  $\geq 3$  AE is observed, will continue on the same dose of ruxolitinib **plus** oral belumosudil 200 mg QD (or BID if receiving concomitant PPI) starting on C2D1.

In the event that the participant is experiencing Grade  $\geq 3$  AE(s) at the intended C2D1 visit assessment, treatment with belumosudil should not begin. This visit will be considered an unscheduled visit and the C2

D1 visit should be rescheduled. The participant can continue on ruxolitinib alone and should be followed for resolution of the Grade  $\geq 3$  AE(s). If the Grade  $\geq 3$  AE(s) improves to Grade  $\leq 2$  or resolves completely within 4 weeks, the participant will still be eligible to receive belumosudil. In this case, they should come back in for a true C2D1 visit and can complete all the necessary assessments as well as belumosudil dosing. If the Grade  $\geq 3$  AE(s) does not recover within 4 weeks, the participant will complete the End of Treatment visit and discontinue study. If there are any questions or concerns about the patient status and treatment in these scenarios, this should be discussed with the sponsor.

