### **10.7 Adverse Event Reporting Period and Follow up of AEs, SAEs, and AESIs**

The AE reporting period begins at the time the patient receives their first dose of study treatment (i.e., C1D1). All AEs, SAEs and AESIs must be followed until resolution or 28 days following the last dose of study treatment, whichever comes first. The QI shall provide follow-up information when available in a new follow-up SAE form. Resolution status of such an event should be documented on the eCRF.

Patients withdrawn from the study due to an AE will be followed until the AE has resolved. In the case of an SAE, the patient will be followed until clinical recovery or until progression has been stabilized or judged to be chronic. After discontinuation from protocol treatment, all patients will be followed for any ongoing or late toxicities. Patients will be seen for a Safety Follow up visit,  $28 \pm 7$  days after discontinuing treatment. Safety Follow up procedures will be completed as indicated in the Study Calendar.

The AE reporting period will end once 28 days have passed since the patient's last dose of study drug. Therefore, SAEs occurring after the last dose of study treatment that have been deemed by the QI as at least possibly related to protocol treatment, must be reported if it occurs within 28 days after discontinuation of the investigational products. In addition, any known untoward event of any severity that occurs subsequent to the AE reporting period that the Investigator assesses as at least possibly related to the study therapy (i.e., the relationship cannot be ruled out) should also be reported as an AE. Ongoing and non-resolved toxicities are followed until resolution back to baseline or  $\leq$  Grade 1 after off treatment, or until considered stable by the QI.

---

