Safety and tolerability (primary endpoint) will be assessed throughout the treatment duration using CTCAE v5.0 grading. Adverse events will be summarized descriptively, including: - Incidence (number and percentage) of AEs, SAEs, and AESIs by grade, system organ class, preferred term, and relationship to study drug (belumosudil, ruxolitinib, or combination). - Frequencies and percentages for AEs leading to dose modifications, interruptions, or discontinuations. - Time-to-first AE (for key events) using Kaplan-Meier estimates if appropriate. No formal hypothesis testing will be performed for safety; results will be presented in tabular and graphical formats.

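### The only safety population requires a belumosudil dose, so patients who die or stop on ruxolitinib alone are left out of the primary adverse event tables

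*Protocol*

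**What the plan says.** Section 11.2 of the protocol defines three populations. The safety population is "All enrolled patients who received at least one dose of belumosudil", and the same section settles its use: "The population evaluable for safety will be the safety population". The synopsis gives the same definition. No AE analysis is assigned to the ITT population or to any other set.

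Belumosudil is not where treatment starts. Under Section 5.1, participants "will be started on ruxolitinib monotherapy orally at the standard recommended dose of 10 mg BID for 4 weeks", and belumosudil is added at C2D1. Section 10.7 ties safety collection to the earlier date: "The AE reporting period begins at the time the patient receives their first dose of study treatment (i.e., C1D1").

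Section 5.1, repeated in a footnote to the Section 8 calendar, makes the second drug conditional. If a Grade ≥3 AE is present at the intended C2D1 visit, "treatment with belumosudil should not begin". The patient may stay on ruxolitinib alone while the event is followed. If it "does not recover within 4 weeks, the participant will complete the End of Treatment visit and discontinue study".

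On the analysis, Section 11.3.1 states: "Safety and tolerability (primary endpoint) will be assessed throughout the treatment duration using CTCAE v5.0 grading". It lists AEs, SAEs and AESIs by, among other things, "relationship to study drug (belumosudil, ruxolitinib, or combination"), and asks for AEs leading to dose modification, interruption or discontinuation.

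**The concern.** The analysis set starts at a later point in treatment than the endpoint it serves. Every patient spends at least the first cycle on ruxolitinib alone, with AEs collected from the first dose, but enters the safety set only on reaching belumosudil. One of the routes by which a patient fails to reach it is a persisting severe AE. Membership of the set therefore depends partly on the outcome that the set is meant to measure.

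At stake is a primary endpoint, safety and tolerability. A patient taken off study for an unresolved Grade ≥3 event is a clear tolerability failure of the regimen as given, and Section 11.3.1 asks for AE-related discontinuations to be tabulated. Under the Section 11.2 definition that patient appears in neither the numerator nor the denominator. The same holds for a patient who dies during the ruxolitinib-alone period.

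**Working it through.** The protocol states no figure on this point, so there is none to reproduce. The check is a trace through the sections, followed by arithmetic on assumed counts.

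**Trace for one patient**

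1. Enrolled and starts ruxolitinib at C1D1 (Section 5.1). AE reporting is open (Section 10.7).
2. Has a Grade ≥3 AE at the intended C2D1 visit. Belumosudil is withheld (Section 5.1). The rule does not ask about cause.
3. The event does not improve to Grade 2 or lower within 4 weeks. The patient has the End of Treatment visit and leaves the study, after about 4 + 4 = 8 weeks of ruxolitinib and no belumosudil.
4. The patient is not replaced, because Section 5.7 replaces only those who received no study drug at all. The patient therefore remains one of the 63.
5. The patient fails the Section 11.2 condition and is outside the AE tables.

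A patient whose event does improve within the 4 weeks starts belumosudil and stays in the safety set. A patient who dies or withdraws on ruxolitinib alone is also outside it.

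**Size of the effect**

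Inputs:
- N = 63 enrolled (synopsis; Section 11.1).
- k = patients removed by the C2D1 rule (assumed). Each is by definition a Grade ≥3 case and an AE-related discontinuation.
- x = belumosudil-treated patients with at least one Grade ≥3 AE (assumed).
- All other patients are assumed to receive belumosudil.

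Rate as written: x / (63 − k)

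Rate with everyone dosed: (x + k) / 63

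Difference: (x + k)/63 − x/(63 − k) = k(63 − k − x) / [63(63 − k)]

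Since x cannot exceed 63 − k, the difference is never negative. It is zero only if every belumosudil-treated patient also has a Grade ≥3 AE.

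| k | x | As written | All dosed | Difference |
|---|---|---|---|---|
| 1 | 15 | 15/62 = 24.2% | 16/63 = 25.4% | 1.2 points |
| 3 | 15 | 15/60 = 25.0% | 18/63 = 28.6% | 3.6 points |
| 6 | 15 | 15/57 = 26.3% | 21/63 = 33.3% | 7.0 points |
| 1 | 20 | 20/62 = 32.3% | 21/63 = 33.3% | 1.1 points |
| 3 | 20 | 20/60 = 33.3% | 23/63 = 36.5% | 3.2 points |
| 6 | 20 | 20/57 = 35.1% | 26/63 = 41.3% | 6.2 points |

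The same formula applies to AE-related discontinuation, with x then counting such discontinuations among belumosudil-treated patients.

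**Where the direction reverses**

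For belumosudil-related or combination-related AEs, a patient never given belumosudil cannot add to the numerator. With y such patients, the rate as written is y/(63 − k), and widening the denominator gives y/63, which is lower. With y = 15 and k = 6, that is 15/57 = 26.3% against 15/63 = 23.8%. For these rates the belumosudil-treated patients are the right denominator.

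**The case against.** The strongest case on the other side starts from the primary objective (Section 3), which concerns the combination of belumosudil with ruxolitinib. Belumosudil is the investigational product and ruxolitinib is given as standard of care. A patient with no belumosudil has no combination exposure, so a belumosudil-exposed set is a natural denominator. This stands as a reason to keep such a set. It does not justify making it the only one, because Section 11.3.1 covers the whole treatment duration and tabulates relationship to ruxolitinib, and Section 10.7 starts the clock at C1D1.

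Second, nothing is lost from the record. AEs are collected from C1D1, SAEs and AESIs are reported (Section 10.8), deaths from the first dose of study therapy are reported promptly (Section 10.4), and the DSMB reviews safety data (Section 5.8). The opening of Section 11 also summarises permanent discontinuations with reasons, without limiting this to the safety population. All of that stands. A reader might infer that these patients disappear from the study; they do not. What they are missing from is the primary AE tables.

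Three other stronger readings are tempting and are not supported:
- *That the excluded patients are those with ruxolitinib toxicity.* The C2D1 rule applies to any Grade ≥3 AE whatever its cause, and only to those that persist. Deaths and withdrawals for other reasons are excluded too.
- *That all AE rates are biased downward.* The direction is assured only for all-cause Grade ≥3 incidence and AE-related discontinuation, and only for patients removed by the C2D1 rule. Patients who stop early for reasons other than an AE need not push rates either way, and events that need longer exposure may be rarer in this group.
- *That Cycle 1 and combination-period AEs will be pooled without distinction.* The protocol does not say so, and a split by period is commonly left to a statistical analysis plan.

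Finally, the size is unknown, and k = 6 equals the whole planned dropout allowance (63 − 57 = 6, Section 11.1), so it is a high case. Safety carries no formal test, and the success rule counts responders only, so the efficacy decision is not touched.

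**Conclusion.** The definition is wrong as written. The protocol itself fixes it, in Section 11.2 and in the synopsis, so a statistical analysis plan that used another set would contradict it. It leaves out of a primary endpoint a group of treated patients, some of whom are excluded because of severe AEs.

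For those removed by the C2D1 rule, the direction of the error in all-cause Grade ≥3 incidence and AE-related discontinuation over the regimen follows from the definitions and needs no assumption. The size does: roughly 1 point for one excluded patient and 6 to 7 points for six, with 15 or 20 Grade ≥3 cases assumed among those given belumosudil. The protocol gives neither count. The conclusion does not extend to AEs attributed to belumosudil or the combination, and it concerns descriptive tables, not data capture or the efficacy test.

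**What to change.** In Section 11.2 and the synopsis together, define the safety population as all enrolled patients who take at least one on-study dose of ruxolitinib or belumosudil. In Section 11.3.1:

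- report AEs for the whole regimen in that population;
- report them also by period: ruxolitinib alone, and from the first belumosudil dose;
- keep belumosudil-treated patients as a named subset, and use it as the denominator for the combination period and for belumosudil-related or combination-related AEs.

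No new data, visits or patients are needed. The cost is one definition changed in two places and one extra split in the AE tables. Overall AE rates may look slightly worse than under the present definition.

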### **11.1 Study Design and Justification for Sample Size**

Based on the REACH3 study, the overall response rate with Ruxolitinib monotherapy was 49% at 6 months. Our null and alternative hypothesis was 49.7% and 66% of ORR at 6

months, respectively. For a sample size of 57 observations, a 2-sided exact test as the power calculation method will have 90% power to reject the null hypothesis assuming that the null proportion is 0.497, the alternative proportion is 0.66, and that the test is conducted at the alpha 10% significance level. Considering a 10% drop outs the study will enrol 63 pts.

If the number of patients achieving CR or PR at 6 months is 37 or more, the hypothesis that  $P \leq 0.497$  is rejected. Thus, success of the trial will be defined as 37 or more patients achieving CR or PR at 6 months out of 63 patients, which can be translated into a clinically meaningful improvement over standard care and within the expected safety profile. If the number of patients achieving CR/PR at 6 months is 36 or less, the hypothesis that  $P \geq 0.66$  is rejected, thus determined to be failure.

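### Power for the primary ORR rests on 57 patients and success is judged out of 63, while the set labelled evaluable for response leaves out early failures

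*Protocol*

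**What the plan says.** Protocol section 11.1 states the power on one number: "For a sample size of 57 observations, a 2-sided exact test as the power calculation method will have 90% power", "assuming that the null proportion is 0.497, the alternative proportion is 0.66", with "the test is conducted at the alpha 10% significance level". It then adds an allowance: "Considering a 10% drop outs the study will enrol 63 pts". The decision rule uses the larger number: "success of the trial will be defined as 37 or more patients achieving CR or PR at 6 months out of 63 patients". A count of 36 or fewer is failure.

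Section 11.2 opens with "The following study populations are defined and will be analysed as specified below". It defines the ITT population as "The total population of patients enrolled in the study" and the Efficacy population, labelled evaluable for response, as "All enrolled patients who complete at least one cycle of belumosudil treatment with adequate baseline disease assessment". The synopsis repeats both definitions.

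Section 11.3.1 gives the ORR as a proportion with an exact 95% confidence interval and names no population. Nothing says how a patient without a response assessment at C8D1 (24 weeks of combination therapy) is counted.

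**The concern.** In a single-arm trial tested against a fixed rate, the denominator is part of the hypothesis. Here the power, the success rule and the label evaluable for response point to three different groups.

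The Efficacy population is selected on early outcome. Belumosudil starts at C2D1, week 4, after a 28-day ruxolitinib cycle (sections 1.3 and 5.1). Completing one belumosudil cycle therefore takes a patient to about week 8, or later if C2D1 is deferred. Under section 5.1, a patient whose Grade 3 or higher adverse event does not recover within 4 weeks never starts belumosudil and leaves the study. Patients who die, or who stop for new systemic treatment, before completing that cycle are also outside the set, although section 9 classes new systemic cGvHD therapy as treatment failure. No control arm loses patients in the same way.

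Two things are at stake: whether the trial has the power it claims, and whether the reported ORR can be set fairly against 49.7%.

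**Working it through.** **Inputs.** From section 11.1: null p0 = 0.497, alternative p1 = 0.66, n = 57, N = 63, dropout 10%, cut 37. Assumptions: dropout of 5% and 15% around the stated 10%, and 3, 6 or 9 patients outside the Efficacy population, whose size the protocol does not give. Tail probabilities are exact binomial, P(X ≥ c | n, p). Confidence intervals are Clopper-Pearson.

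**1. The plan's own figures.**

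- Two-sided 10% exact test at n = 57 (upper tail at most 5%): cut 36. P(X ≥ 36 | 57, 0.497) = 2.8% and P(X ≥ 36 | 57, 0.66) = 72.6%. The stated 90% is not reproduced.
- One-sided 10% exact test at n = 57: cut 34, alpha 8.5%, power 87.5%. A one-sided 10% normal approximation gives 89.3%, the closest match.
- Enrolment: 57 × 1.1 = 62.7 and 57 / 0.9 = 63.3, so 63 is 57 with the dropout allowance added.
- Cut of 37 on all 63: P(X ≥ 37 | 63, 0.497) = 9.5% and P(X ≥ 37 | 63, 0.66) = 91.0%. The cut is that of a one-sided 10% exact test on 63 patients, not on 57.

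**2. Power to reach 37 when there is dropout.**

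| Meaning of 66% | Calculation | Power |
|---|---|---|
| Rate among all 63 | P(X ≥ 37 \| 63, 0.66) | 91.0% |
| Rate among those who remain; exactly 57 remain | P(X ≥ 37 \| 57, 0.66) | 62.8% |
| Same; random 5% dropout counted as failure | 0.66 × 0.95 = 0.627; P(X ≥ 37 \| 63, 0.627) | 78.4% |
| Same; random 10% | 0.66 × 0.90 = 0.594; P(X ≥ 37 \| 63, 0.594) | 59.6% |
| Same; random 15% | 0.66 × 0.85 = 0.561; P(X ≥ 37 \| 63, 0.561) | 38.6% |

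**3. Effect on the reported estimate.** Take 37 responders and exclude non-responders only.

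| Excluded | ORR | 95% CI |
|---|---|---|
| 0 | 37/63 = 58.7% | 45.6 to 71.0 |
| 3 | 37/60 = 61.7% | 48.2 to 73.9 |
| 6 | 37/57 = 64.9% | 51.1 to 77.1 |
| 9 | 37/54 = 68.5% | 54.4 to 80.5 |

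With 6 excluded, the lower limit moves from below 49.7% to above it on the same 37 responders. A result at the null moves too: 31/63 = 49.2% becomes 31/57 = 54.4%.

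**4. Effect on the count-based verdict.** Suppose the true rate among all patients is 49.7% and the excluded patients are all non-responders. With 10% excluded, the rate in the remaining 57 is 0.497 / 0.90 = 0.552, and P(X ≥ 37 | 57, 0.552) = 9.0%. With 15% excluded, it is 0.497 / 0.85 = 0.585 in 54, and P(X ≥ 37 | 54, 0.585) = 8.5%. Neither exceeds the 9.5% on all 63. At the written cut, exclusion does not raise the false-positive rate.

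**The case against.** The strongest reply is that the numbers fit together. The 63 is the 57 with a dropout allowance, the rule names 63, and 63 is the planned ITT set. On that reading 37 of 63 has 91.0% power. This stands as far as it goes: 57 and 63 do not contradict each other as counts. But it needs 66% to be the rate with dropouts already counted as failures, and in that case no allowance for lost observations was called for. Adding one implies that dropouts yield no observation, and the rule then asks the remaining patients to supply all 37 responders.

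Three stronger readings are tempting, and the protocol does not support them.

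- A reader might infer an inflated type I error. Figures of 14% (cut 36 on 57) or 30% (cut 34 on 54) come from cuts re-derived for the smaller set. Section 11.1 classes both 36 and 34 as failure.
- A reader might infer that the same data pass on one set and fail on the other. Removing non-responders cannot change a count of responders. Only the confidence interval shifts against 49.7%, and the rule does not use the interval.
- A reader might infer that everyone outside the Efficacy population is a non-responder. The set also requires an adequate baseline assessment, which is not an outcome. Under section 5.6 removal for progression is discretionary, and some patients without response may continue. Step 3 is therefore the upper end of the effect for each number excluded.

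It is also fair to say that assigning populations to endpoints is often left to the SAP, which is not at hand. The mismatch between power, rule and labelled set is nevertheless in the protocol's own text. Finally, the shortfall to 72.6% for a two-sided exact test at 57 is a separate fault of sidedness and should not be charged to the denominator.

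**Conclusion.** The point holds in two parts.

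First, the stated 90% power and the 37-of-63 rule agree only if 66% is the response rate among all enrolled patients. If 66% describes those who remain and the plan's own 10% drop out, the power to reach 37 is 59.6% to 62.8%. The protocol does not say which is meant.

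Second, reporting ORR on the set labelled evaluable for response would bias the estimate and its interval upward, by up to about 6 percentage points with 6 exclusions (64.9% against 58.7%). That rests on the assumption that those excluded are non-responders. The protocol does not give the benchmark's own denominator or time origin, so no closer comparison with 49.7% is possible.

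The pass or fail decision at the fixed cut of 37 is not distorted by the exclusions. The harm is to the claimed power and to the reported ORR.

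**What to change.** In sections 11.1 to 11.3 and the synopsis:

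- Make the primary ORR set all enrolled patients who received at least one dose of study treatment, with a fixed denominator. Section 5.7 already replaces patients withdrawn before any dose.
- Count as non-responders patients with no C8D1 response assessment, and those with death, discontinuation or new systemic cGvHD therapy before C8D1.
- Apply the success cut to that same N, and say which cut applies if the dosed number is not 63.
- Restate alpha, sidedness and power for that N and cut, with dropouts counted as failures. For orientation, 37/63 has one-sided alpha 9.5%, and power of 91.0% only if 66% is the rate in the whole set. A two-sided 10% exact test on 63 needs 39 responders, with an upper tail of 3.5% and power of 79.5% under the same condition.
- Use the Efficacy population for sensitivity analysis only.

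Keep enrolment at 63. Removing the 10% allowance would leave 57 patients, where exact power is 72.6% (cut 36) or 87.5% (one-sided 10%, cut 34).

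The cost is a few sentences. The reported ORR and the stated power will be somewhat lower.
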